The centralization of esophageal and gastric cancer surgery in Spain is now a reality in Catalonia and Navarre since 2011 and 2012 respectively. Since 2013, the Spanish EURECCA Esophagogastric Cancer Registry has been collecting data in both Autonomous Communities (Allum 2016) and, furthermore, it is important to point out that since the beginning there has been a consensus on the required variables with their respective definitions. An example of this has been the description and reporting of post-operative complications following the recently validated recommendations of the Esophageal Complications Consensus Group (ECCG) (Low 2015; Low 2018).

Verifying and validating the collected data is crucial to ensure the reliability of the information (Bray 2009; Parkin 2009). In Norway, an audit of the data collected in the Norwegian Registry of Rectal Cancer (NRCR) created in 1993 (Sunniva 2015) has been published, demonstrating a high degree of validity and an improvement in the quality of the treatment over the years. Since June 2012, this registry also has an electronic version. In relation to esophagogastric cancer surgery, periodic audits on the diagnostic process and the results of the treatment are carried out in England, Sweden (Linder 2016), and the Netherlands (Busweiler 2016). All these publications conclude that audits are an important strategy used in health care to maintain quality standards and improve patient care. Audits provide a way to identify deficiencies in clinical practice, to assess trends and provide constructive feedback to surgeons and others health care workers. The validity of any audit is based on the accuracy of its data. For this reason, is considered vital to carry out an "in situ" audit of the data collected in the EURECCA on-line Registry.

Methodology

The EURECCA Registry

The EURECCA online Registry collects data of esophageal, esophagogastric junction and gastric cancer resectable patients undergoing surgery. It was launched with the initial participation of 2 Spanish Autonomous Communities, Catalonia and Navarra, with 21 participating centers. In March 2017, the Basque Country joined the Registry, incorporating other 9 hospitals. More recently La Rioja joined as well with a single hospital. It is important to highlight that, to date, there are 30 participating centers in the Spanish EURECCA Esophagogastric Cancer Registry, which collect information of more than 10 million people.

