To ensure that patients are collected consecutively (non-selected) and the Registry includes all cases of resectable Esophageal, Esophagogastric junction and Stomach Cancer operated on, a cross-check with the data from the Clinical Documentation Service of each center will be carried out. Each Clinical Documentation Service will be requested to perform a search in its hospital discharge database of all cases codified by the International Classification of Diseases (ICD-9-CM International Classification of Diseases, Ninth Revision, Clinical Modification for Catalonia and ICD-10-CM International Classification of Diseases, Tenth Revision, Clinical Modification for Navarra) with the main diagnosis associated with Esophageal, Esophagogastric junction and Stomach Cancer.

- Second level: Accuracy.

A small group of researchers (2 doctors or 1 doctor + 1 Data manager), from a different center to the one evaluated, will visit the audited center and will carry out an exhaustive review of a list of selected

variables included in the Registry. A random sample of patients will be selected in each participating center.

- For those centers where the total number of cases is less than or equal to 20, the entire sample (100%) will be analyzed.
- For those centers where the total number of cases is between 21 and 100, a sample of 20 patients will be taken, randomly chosen (minimum 20%).
- For those centers that exceed 100 cases, a sample of 20% of the total number of patients included in that hospital will be selected, up to a maximum of 50 patients.

The following variables will be analyzed:

- Comorbidities: ASA (American Society of Anesthesiologists) score, Charlson Comorbidity Index.
- Diagnosis and stage: Date of diagnosis, Location of the tumor.
- Neoadjuvant treatment: Start date.
- Surgery: Date of the surgery, Access, Surgical technique (type of gastrectomy and esophagectomy).
- Histopathology: Histological type, Radically of the resection (R0, R1, R2), No. of lymph nodes examined, Pathological stage (pTNM).
- Postoperative period: Complications, Transfusion, Pneumonia, Anastomotic leak, Clavien-Dindo classification.
- Follow-up: Last follow up, Readmission, Recurrence, Date of recurrence, Patient status, Date of death.

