A concordance process between the extracted data during the "in situ" review and the data contained in the EURECCA Registry will be established. The reviewers will prepare an audit report with the errors and/or blank fields detected and this will be sent to the PIs of this audit for its analysis.

Statistical analysis plan

Univariate descriptive analysis will be performed, presenting the results as means (with standard deviation and range) for the continuous variables and as numbers and percentages for the categorical variables. In addition, bivariate analysis will be carried out among the variables of interest to describe their level of correlation and evaluate the possible differences between them. To evaluate the differences between the continuous variables, the comparison of means based on the T-Student will be used, and for the comparison of differences in the categorical variables, the Chi-square test will be used. Finally, linear regression models and generalized linear models (as appropriate depending on the response variable) will be used to study the dependence of the variables of interest, with other factors of study. Statistical analysis will be carried out using the SPSS (Statistical Package for the Social Sciences) Software (IBM SPSS Statistics 22). All tests will be bilateral with a level of significance of 5%. 100% of the data recorded from 01/01/2014 to 06/30/2017 will be analyzed, and the proportion of values lost in the variables of interest will be evaluated.

In particular, it is proposed to carry out the following descriptive and comparative analysis between hospitals:

- Tumor location: Stomach, Esophagus, Esophagogastric junction.
- Patients characteristics and comorbidities: Age (≤ 70 o > 70), Sex (Ratio M:F), BMI (< 20 , $20-24$, $25-29$, ≥ 30), Weight loss %, ECOG (Eastern Cooperative Oncology Group) score, ASA score (1-2 or ≥ 3), Charlson Comorbidity index (0, 1, ≥ 2).
- Tumor characteristics: Tumor localization, Histological type, Clinical tumor stage, CEA (carcinoembryonic antigen), Ca 19.9, Preoperative study.
- Treatment: Preoperative optimization (transfusions, hemoglobin (Hb) at diagnosis, preoperative Hb, iron therapy), Neoadjuvant treatment, Surgery (type, approach, type of anastomosis, etc.)
- Histopathology.
- Postoperative period and follow-up: Length of hospital stay, Complications (types and Clavien-Dindo classification), Readmission, Adjuvant treatment, In-hospital mortality, 30 and 90 days mortality, Recurrence.

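### Chi-square is the only test named for comparing hospital mortality, yet the plan allows for small and very uneven centres, so the 5% level is not assured in sparse tables

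*Combined protocol and SAP*

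**What the plan says.** The Statistical analysis plan names one test for all categorical variables: "for the comparison of differences in the categorical variables, the Chi-square test will be used". All tests are two-sided at 5%. The section then states that "it is proposed to carry out the following descriptive and comparative analysis between hospitals", and the list that follows includes "In-hospital mortality, 30 and 90 days mortality, Recurrence". Categorical results are to be shown as numbers and percentages. No exact test, expected-count rule, interval, control limit or multiplicity rule is given. The plan does not say whether hospitals are compared in one overall test, in pairs, or each against the rest.

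The Methodology section (The EURECCA Registry) describes a launch in "Catalonia and Navarra, with 21 participating centers", and the analysis is limited to those two regions.

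Under Audit and validation (second level, Accuracy), the sampling rules are split by centre caseload. One reads "For those centers where the total number of cases is less than or equal to 20, the entire sample (100%) will be analyzed". There is a middle band of 21 to 100 cases, and the top band begins "For those centers that exceed 100 cases, a sample of 20% of the total number of patients included in that hospital will be selected".

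**The concern.** The chi-square test relies on a large-sample approximation. With uncommon outcomes and small centres, the expected number of deaths per centre is low. When centre sizes are also very unequal, the true error rate of the test can drift from its nominal level. The sampling bands show that the authors allowed for both small and unequal centres.

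The project aims to make outcomes comparable between centres and to give the Registry credibility for later studies. A between-hospital mortality p-value that does not have its stated meaning would undercut that aim. Hospital percentages shown without any measure of uncertainty are also easily over-read.

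**Working it through.** **Inputs from the documents.** Chi-square test, two-sided 5%, 21 centres, caseload bands of up to 20, 21-100 and over 100. The comparisons use all registered cases, so centre size means full caseload and not the audit sample.

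**Assumptions.** No caseload or event rate is stated. Mortality is taken as 2-5% and the same in every hospital, with several sets of 21 centre sizes. The plan reports no figure here to reproduce beyond the nominal 5%.

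**Step 1: expected deaths, E = n × p.**
- 20 cases: 20 × 0.02 = 0.4; 20 × 0.05 = 1.
- Cases needed for E = 5: 5 / 0.05 = 100; 5 / 0.02 = 250.

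At 5% mortality, every centre with fewer than 100 cases is below the usual threshold of 5.

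**Step 2: error rate of the overall 21 × 2 test.** The statistic is the sum over centres of (x − n·p̂)² / (n·p̂·(1 − p̂)), where x is deaths and p̂ is the pooled rate, referred to chi-square with 20 degrees of freedom. Deaths were simulated with equal true mortality, in 40,000 datasets per setting.

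| Assumed centre sizes | Rejection at nominal 5%, mortality 2-5% |
|---|---|
| 21 × 20 | 4.5-4.8% |
| 21 × 100 | 4.6-4.9% |
| 3 × 20, 12 × 60, 6 × 150 | 5.2-6.0% |
| Geometric, 12 to 260 | 6.0-7.1% |
| Geometric, 8 to 300 | 6.1-8.1% |
| 5 × 10, 4 × 20, 8 × 80, 4 × 200 | 6.3-8.4% |
| 6 × 5, 5 × 15, 6 × 80, 4 × 250 | 8.0-10.6% |

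In each uneven set the higher figure belongs to 2% mortality. The first row shows that low expected counts alone do not inflate the overall test; unequal sizes do.

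**Step 3: two small equal centres.** Exact enumeration for 20 against 20 cases gives an error rate of 0.1% at 2% mortality, 1.2% at 5% and 3.9% at 10%. Here the test errs in the other direction.

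**Step 4: spread of crude rates.** With a true 5% everywhere and sizes from 12 to 260, some centre shows 10% or more in over 80% of datasets. The median highest rate is about 13% and the median lowest is 0%. A 20-case centre has no deaths with probability 0.95²⁰ = 36%.

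**Step 5: what an exact test does and does not repair.** A Monte Carlo exact overall test (1,500 datasets per setting, simulation standard error √(0.05 × 0.95 / 1500) = 0.6 points) rejects in 3.9-6.4%, in line with 5%. If instead each centre is tested against the rest at 5%, at least one is flagged by chance in 57-81% of registries with chi-square. That remains 60-65% when every centre has 100 cases, and 35-59% with Fisher's test. For 21 independent tests the figure would be 1 − 0.95²¹ = 66%. With Fisher's test at 0.05 / 21 it falls to about 2-4%.

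**The case against.** The strongest reply is that the size of the problem rests on inputs the documents do not give. The bands are conditional rules for drawing the audit sample: they show that small centres were allowed for, not that any exist. The background also says that this surgery was centralised in both regions from 2011 and 2012, which argues against assuming many tiny centres. At 5% mortality and moderate unevenness the error rate is barely above nominal. All of this stands.

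Three stronger readings are tempting and should not be drawn.
- *The 5% level is missed.* Several plausible size mixes give about 5%, and some comparisons give less.
- *Chi-square causes the chance extremes.* These come from small numbers and many hospitals, and they persist with centres of 100 cases and with Fisher's test.
- *Two deaths in a 20-case centre would mark it as an outlier.* At a true 5%, two or more deaths have probability 1 − 0.95²⁰ − 20 × 0.05 × 0.95¹⁹ = 26%. Against a large remainder, z = (0.10 − 0.05) / √(0.05 × 0.95 / 20) = 1.03, p about 0.30.

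The plan also sets no ranking or outlier rule, so misreading of extremes is a possibility and not a planned step.

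The planned generalized linear models do not answer the point. No centre term, random effect or sparse-data method is specified, and they do not replace the named test.

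**Conclusion.** The concern holds in a limited form. Chi-square is the only named test for sparse between-hospital mortality tables, and its 5% level is not assured there. Under the assumptions of 21 centres and 2-5% mortality, the overall test's error rate runs from about 4.5% to 10.6%. Where it falls depends almost wholly on how uneven the centres are, which the documents do not report. Wide chance spread in crude hospital rates is a separate matter that a change of test alone would not cure. This is a cheap improvement to the plan and not a demonstrated failure of it.

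**What to change.** Add to the Statistical analysis plan:

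*Where expected counts are below 5, hospital comparisons use an exact or Monte Carlo exact (Fisher-Freeman-Halton) test instead of chi-square. Hospital mortality counts and percentages are shown with exact binomial intervals, or on a funnel plot with exact limits around the overall rate, and no hospital is singled out unless it lies outside limits that allow for the number of hospitals compared.*

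The plan should also say whether hospitals are compared in one overall test, in pairs, or each against the rest.

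The cost is a short addition to the text and one figure or a set of intervals, with no extra patients or data. The exact test is slightly conservative. The planned numbers and percentages are kept.

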For this specific project, only the cases of the two first Autonomous Communities that initiated the project will be analyzed: Catalonia and Navarre.

Quality measure and data set

For this specific study the data collection was closed on December 31, 2017.

The online form contains 93 variables distributed in 4 categories of data:

- Patient characteristics: Patient data (7) and Comorbidities (5).
- Care process: Diagnosis and staging (10), Preoperative optimization (4), Neoadjuvant treatment (3).
- Surgery and histopathology: Surgery (17), Histopathology (24).
- Postoperative period: Hospital stay and Complications (14), Follow-up (9).

The selection of these variables was established in accordance with a general consensus of the Spanish EURECCA group. Multidisciplinary quality standards have been introduced (surgery, oncology and histopathology) and all the PIs (Principal Investigators) were sent the definitions of many of the variables: for instance lymphadenectomies (D0, D1, D1+, D2) and complications (Pneumonia, Acute respiratory distress syndrome, myocardial infarction, acute delirium, generalized sepsis, pancreatic fistula). In addition, pathologists from all Units participating in the EURECCA project agreed to follow standardized histopathology protocols for esophageal, esophagogastric junction and gastric cancer in order to describe and report their findings.

Audit and validation

The on-line form itself is considered as an internal filter/audit for data collection. Several data fields inform if they seem implausible when saving them, according to previously established ranges.

In addition, the Data Manager (DM) monthly provides a feedback to each center, summarizing the missing variables (blank) and potentially erroneous ones, to be reviewed by the PIs.

Based on the experience of the Dutch Upper Gastrointestinal Cancer Audit (DUCA) (Busweiler 2016), the validation of the data collected in our Registry will be carried out at two levels:

- First level: Integrity.

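### Pooled association tests make no provision for correlation within about 21 hospitals, so their 5% level is not secured when both factor and outcome vary by hospital

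*Combined protocol and SAP*

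**What the plan says.** The Statistical analysis plan has three layers of inference beyond description.

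- Associations between pairs of variables: "bivariate analysis will be carried out among the variables of interest to describe their level of correlation" and to assess differences. For continuous variables "the comparison of means based on the T-Student will be used"; "for the comparison of differences in the categorical variables, the Chi-square test will be used".
- Models: "linear regression models and generalized linear models (as appropriate depending on the response variable) will be used to study the dependence of the variables", set against further study factors. The covariates are not listed.
- A separate list of descriptive and comparative analyses in which hospital is the grouping factor.

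One error rate covers all of this: "All tests will be bilateral with a level of significance of 5" per cent.

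On the source of the patients, the section on the EURECCA Registry says that "only the cases of the two first Autonomous Communities that initiated the project will be analyzed", and that the registry was launched in "Catalonia and Navarra, with 21 participating centers". It later says that "to date, there are 30 participating centers", whereas its own regional counts sum to 21 + 9 + 1 = 31. The number of hospitals in this study is therefore 20 or 21.

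No section mentions stratification by hospital, a hospital effect, generalised estimating equations (GEE) or a cluster-robust variance. Differences between centres appear under Limitations only as a matter of coding.

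**The concern.** In their usual form, the named methods treat patients as independent. Patients treated in one hospital share surgeons, pathways, case mix and recording habits, so their outcomes may be correlated. That alone does not disturb a test of a factor spread evenly over hospitals. It matters when the factor is clustered too. Surgical approach, type of anastomosis, iron therapy and neoadjuvant treatment are plausible examples of practices that a hospital largely sets.

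Two things then happen. The naive standard error is too small, because patients who share both the practice and the hospital carry less than independent information. Hospital also becomes a confounder: the pooled association mixes the contrast within hospitals with whatever else separates hospitals that favour the practice from those that do not.

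At stake is whether an association between a practice and an outcome, reported as significant at 5%, carries the error rate claimed for it. The protocol's case for the registry rests on its credibility as a source for later publications.

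**Working it through.** **Inputs from the document.** Two-sided level 5%; about 21 hospitals; t and chi-square tests without covariates; model covariates open. Cases per hospital are not given. The audit sampling bands provide for centres with up to 20, 21–100 and more than 100 cases. The cap of 50 audited patients is reached at 50 / 0.20 = 250 cases. No ICC is given.

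**Inputs assumed.** Hospital sizes, the ICC of the outcome and the ICC of the factor (the exposure ICC).

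**Step 1: formula.** With m cases per hospital of equal size,

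DEFF = 1 + (m − 1) × ICC(factor) × ICC(outcome)

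actual level = 2 × [1 − Φ(1.96 / √DEFF)]

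With no clustering DEFF = 1 and the level is 2 × [1 − Φ(1.96)] = 5.0%, the plan's own figure.

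Worked case: m = 50, factor ICC 0.3, outcome ICC 0.10. DEFF = 1 + 49 × 0.03 = 2.47; 1.96 / √2.47 = 1.247; level 21.2%.

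Ranges for outcome ICC 0.01 to 0.10:

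| Factor ICC | m = 20 | m = 50 | m = 100 |
|---|---|---|---|
| 0 | 5.0% | 5.0% | 5.0% |
| 0.1 | 5.2–7.2% | 5.6–10.8% | 6.2–16.5% |
| 0.3 | 5.7–11.8% | 6.7–21.2% | 8.5–32.5% |
| 1 (fixed by hospital) | 7.2–25% | 10.8–42% | 16.5–55% |

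**Step 2: simulation of the chi-square test.** 21 hospitals of 12 to 260 cases, geometrically spaced (1,752 in all); outcome about 40%; no true effect. Hospital log-odds vary with standard deviation SD, so outcome ICC = SD² / (SD² + 3.29): 0.003 for SD 0.1, 0.012 for 0.2, 0.027 for 0.3, 0.046 for 0.4 and 0.071 for 0.5. The factor's prevalence per hospital is Beta(a, a), so its ICC = 1 / (2a + 1): 0.50 for a = 0.5 and 0.20 for a = 2.

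| Setting | Crude chi-square rejects |
|---|---|
| Factor not clustered | 4.7–5.7% |
| SD 0.1, factor ICC 0.05–0.50 | 4.8–7.2% |
| SD 0.2, factor ICC 0.05 / 0.10 / 0.20 | 5.2% / 6.8% / 8.0% |
| SD 0.3, factor ICC 0.05 / 0.10 | 6.7% / 8.1% |
| SD 0.3, factor ICC 0.20–0.50 | 12–21% |
| SD 0.4, factor ICC 0.20–0.50 | 16–28% |
| SD 0.5, factor ICC 0.20–0.50 | 20–37% |

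With a factor ICC of 1 / 11 ≈ 0.09 (a = 5), the rate reached 6–13% over the settings tried. Weak clustering of the factor is thus harmless only while outcomes also differ little between hospitals. With a 20% outcome, strongly clustered factors gave 10–14% (SD 0.3) and 15–31% (SD 0.5).

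**Step 3: the t-test.** A separate simulation used hospital sizes with a coefficient of variation of 0.7 and outcome ICC 0.05. With a mean of 50 cases per hospital, the t-test rejected in 8.4%, 16.6% and 34.6% for factor ICC 0.1, 0.3 and 1. The chi-square test under the same design gave 8.6%, 16.1% and 32.6%.

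**Step 4: remedies.**

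- Cochran-Mantel-Haenszel test stratified by hospital: 4.0–6.0%.
- Hospital as a fixed effect, where the factor varies within hospitals: 3.8–6.1%.
- Cluster-robust variance with a t reference on 20 degrees of freedom: about 5–8% for such factors, but 7–10% when the factor is constant within each hospital.

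A random intercept was not simulated.

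**The case against.** The strongest reply is that the plan is mainly an audit and a description. No primary hypothesis depends on these tests, and the plan names no pooled test of a practice against an outcome. The practices given as examples stand in the list of comparisons between hospitals, where hospital is the factor under test and the objection does not arise. Whether such pairs will be tested on pooled data is an inference from the open reference to variables of interest. The covariates are open too, so hospital may well enter the regressions.

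Most of this stands and limits the point. A reader might infer that pooled associations will be declared significant far more often than 5% of the time. The document does not support that: the result turns on ICCs and hospital sizes it does not give, and comparisons among patient traits such as age or sex may be only weakly clustered. Nor can it be said that the models ignore hospital; the accurate statement is that the plan does not say.

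Two parts of the reply do not remove the point. The t and chi-square tests take no covariate, so open model wording cannot rescue them. And a plan that chooses to test, and fixes 5% for all tests, should deliver that level whether or not the tests are its main purpose.

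**Conclusion.** The omission is real and its effect is conditional. For pooled tests of a factor and an outcome that both vary by hospital, the stated 5% is not secured and the estimate is confounded by hospital.

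Under the assumed sizes and a 40% outcome, the crude chi-square level is about 5–8% when the factor is weakly clustered (ICC 0.05–0.10, SD up to 0.3) or when SD is 0.1. It is about 12–37% when the factor is strongly clustered (ICC 0.20–0.50, SD 0.3–0.5), and near 5% when the factor is not clustered. These figures measure false rejection when practice and outcome vary independently across hospitals. If hospitals that favour a practice also differ systematically in outcome, there is a bias that the figures do not include.

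A reader might also infer that the audit findings or the hospital comparison are undermined. They are not: integrity, accuracy, descriptive percentages and the between-hospital analysis do not rest on these pooled tests. The point deserves correction before analysis but does not threaten the study's main aims.

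**What to change.** Add to the Statistical analysis plan, for association tests on pooled patients:

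- Categorical pairs: a Cochran-Mantel-Haenszel test stratified by hospital.
- Comparisons of means, and all linear and generalized linear models: hospital as a fixed or random effect.
- If GEE or cluster-robust variance is used instead: a named small-sample correction for about 21 clusters, since the uncorrected method does not reliably hold 5%.
- Factors that hardly vary within hospitals: a hospital-level analysis, or description only.
- Unadjusted tests may be shown if labelled descriptive.

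The plan already compares hospitals, so hospital is identifiable and no new data are needed. The cost is wider intervals, and little information on factors that are nearly constant within hospitals.

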
Limitations

The Registry requires an effort by all researchers to correctly fill in the data collection form. It is a large number of variables, but validated variables by almost all the PIs and by international consensus have been chosen.

To reduce errors in filling in the data, the open data collection fields have been minimized (which accept any type of character) and closed fields variables have been preferred (drop-down lists and calendars to select the dates).

Another limitation is the variability in the coding used between the participating centers. To reduce this variability to a minimum, the group of researchers developed an exhaustive protocol for defining the variables, which was agreed upon and approved by the research team prior to the start of data collection.

The centralization of the data, leads to the requirement of a secure Internet connection, with an updated browser.

Work plan

The entire project will be carried out at the Hospital del Mar in Barcelona (PSMar), except for the “in-situ” audit of the collected data, which requires a visit of the audit team to each of the participating centers in the project.

The project is structured in two different sub-studies developed in 3 research periods:

1st Period: First 3 months of the study.

During the first period of the study, all cases registered in the online form EURECCA, which underwent surgery from 01/01/2014 until 12/31/2017, will be closed. Each one of the responsible investigators should review the cases before its closing:

- Month 2: Closure of cases operated on from 01/01/2014 until 12/31/2015.
- Month 3: Closure of cases operated on from 01/01/2016 to 12/31/2017.

2nd Period: Next 4 months of the study.

During the second period of the study, the data will be audited for verification and validation at the two levels detailed in the methodology section:

- Months 4 and 5: Extraction of data from the Clinical Documentation Services of each center to check their completeness.
- Months 6 and 7: On-site verification of the data.

3rd Period: Last 5 months of the study.

- Month 8: Statistical analysis.
- Month 9: Conclusions sub-study 1.

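### Recurrence is to be compared between hospitals with no time point and no follow-up cut-off, so a crude percentage would estimate no defined risk

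*Combined protocol and SAP*

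**What the plan says.** The Statistical analysis plan proposes a "descriptive and comparative analysis between hospitals". Its last group, on the postoperative period and follow-up, ends with "In-hospital mortality, 30 and 90 days mortality, Recurrence". Mortality is tied to discharge, 30 days and 90 days; recurrence is tied to nothing.

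The general rules in the same section are:

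- Results are presented "as numbers and percentages for the categorical variables".
- On testing: "for the comparison of differences in the categorical variables, the Chi-square test will be used".
- On models: "generalized linear models (as appropriate depending on the response variable) will be used to study the dependence of the variables of interest".

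No time-to-event method, censoring rule, person-time offset, surgery-year term or minimum follow-up appears in the document.

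Three places bear on a cut-off, and none sets one for recurrence:

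- Quality measure and data set: "For this specific study the data collection was closed on December 31, 2017".
- Statistical analysis plan: "100% of the data recorded from 01/01/2014 to 06/30/2017 will be analyzed".
- Work plan, 1st Period: registered cases "which underwent surgery from 01/01/2014 until 12/31/2017, will be closed", in study months 2 and 3, with no date to which follow-up must run.

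**The concern.** A patient operated on in January 2014 can be observed for up to four years before the end of 2017. One operated on in December 2017 can be observed for days. A percentage pooling them is not a 1-year, 2-year or any other fixed-time risk. Two things follow.

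First, the pooled figure has no clear counterpart elsewhere. Sub-study 2 aims to set the registry's outcomes beside those of other European registries, and a percentage that depends on this registry's own accrual and closing dates does not serve that aim.

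Second, hospitals with the same true risk can differ because their surgery-year mix or follow-up completeness differs. This is conditional: the documents do not show that hospitals differ in these respects. The monthly feedback on blanks, the investigators' review before closing, the on-site audit of last follow-up and the evaluation of missing values can all reduce uneven completeness. None of them gives a 2017 case the follow-up of a 2014 case.

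**Working it through.** The plan states no recurrence rate or follow-up duration, so there is no figure of its own to reproduce. Only the dates come from the document. The recurrence risks, the hazard shapes, even accrual, the surgery-year mixes and the hospital sizes below are assumptions.

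**1. Potential follow-up under each reading of the dates**

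| Reading | Surgery to | Cut-off | Follow-up, days | Months used | Can reach 12 / 24 months |
|---|---|---|---|---|---|
| A | 12/31/2017 | 12/31/2017 | 0 to 1460 | 0-48 | 75% / 50% |
| B | 06/30/2017 | 12/31/2017 | 184 to 1460 | 6-48 | 86% / 57% |
| C | 06/30/2017 | 06/30/2017 | 0 to 1276 | 0-42 | 71% / 43% |

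The shares follow from even accrual: in A, (48 - 12)/48 = 75% and (48 - 24)/48 = 50%.

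**2. Crude percentage, all hospitals together**

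Assume a 2-year risk of 30%.

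- Constant hazard: λ = -ln(0.7)/24 = 0.01486 per month, giving a 1-year risk of 16.3%.
- Front-loaded: F(t) = P(1 - exp(-t/τ)) with P = 0.30/(1 - exp(-24/τ)) and τ from 6 to 18 months, giving a 1-year risk of 26.4% down to 19.8%.

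The crude percentage is the mean of F over follow-up uniform on (a, b). For constant hazard this is 1 - [exp(-λa) - exp(-λb)]/[λ(b - a)]. For reading A: 1 - (1 - 0.49)/0.7133 = 28.5%.

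| Reading | Constant hazard | Front-loaded |
|---|---|---|
| A | 28.5% | 26.2-26.7% |
| B | 32.0% | 28.7-29.4% |
| C | 25.6% | 25.0-26.2% |

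The underlying risk is the same in every row. Only the dates change.

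**3. Two hospitals with equal true risk**

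One has 60% of its cases from 2014-15 and 40% later; the other has the reverse. The spurious gap is 0.2 × (crude in early cases - crude in later cases).

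Reading A, constant hazard: early cases (24-48 months) 1 - (0.70 - 0.49)/0.3567 = 41.1%; later cases (0-24 months) 1 - (1 - 0.70)/0.3567 = 15.9%. The hospitals show 0.6 × 41.1 + 0.4 × 15.9 = 31.0% and 0.4 × 41.1 + 0.6 × 15.9 = 26.0%.

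| Reading | Gap, constant hazard | Gap, front-loaded |
|---|---|---|
| A | 5.0 points | 1.5-3.3 points |
| B | 4.3 points | 0.7-2.5 points |
| C | 4.7 points | 1.9-3.5 points |

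In reading A with a 2-year risk of 20%, the gap is 3.6 points (front-loaded 1.0-2.2). With 50% it is 7.2 (2.5-5.5). With equal mix it is 0.

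**4. Does the remedy work?**

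Recurrence was simulated with an added 10% 2-year risk of death without recurrence (400,000 patients per scenario), and cumulative incidence was estimated by Aalen-Johansen.

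- Non-informative censoring, mixes from 70/30 to 30/70: 1- and 2-year estimates fall within 0.3 points of the truth for all hazard shapes. For constant hazard, truth is 15.9% and 28.6%, and the estimates are 15.9-16.0% and 28.5-28.7%.
- Informative censoring, where event-free patients' last follow-up is out of date, biases the estimate upward:

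| Last follow-up of event-free patients, share of possible time | Observed / possible person-time to 12 months | Bias at 1 year | Bias at 2 years |
|---|---|---|---|
| 75-100% | 0.98 | +0.3 to +0.5 points | +0.7 to +1.2 points |
| 50-100% | 0.95 | +0.8 to +1.1 points | +1.8 to +3.6 points |
| 0-100% | 0.78-0.80 | +4.0 to +5.3 points | +7.9 to +11.6 points |

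**5. Precision for one hospital** (constant hazard, reading A, 4,000 replicates): with 20, 50 and 100 cases the standard error is 8.8, 5.5 and 3.9 points at 1 year, and 12.1, 7.6 and 5.3 points at 2 years.

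**The case against.** The plan never says in terms that recurrence will be compared by chi-square. It allows generalized linear models suited to the response, and last follow-up and date of recurrence are held. That is fair, but no horizon, offset or surgery-year term is given, so the only stated rule for a categorical item is the percentage with chi-square.

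The between-hospital harm is hypothetical and modest. The 60/40 split is assumed. With 100 patients per hospital, the standard error of a crude difference is about 6 points, and the chance of a false significant result rises from 0.05 only to 0.10-0.12 with constant hazard. This stands and limits the weight of the point. It does not touch the other defect: the percentage refers to no defined time even if all hospitals are alike.

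Follow-up may have been updated when cases were closed, after 12/31/2017. With an assumed cut-off of 06/30/2018 and surgery to 12/31/2017, 87.5% can reach 12 months and the gap is 4.6 points with constant hazard, or 0.5-2.4 front-loaded. It is smaller when recurrence is front-loaded, but it remains, and this reading sits poorly with the stated closure of data collection.

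The remedy is sensitive to stale follow-up. Ethical considerations lets each center decide when to complete its data, and the worst-case bias above exceeds the gap being removed. This stands, and is why completeness must be reported with the estimate.

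Finally, the comparison with European registries does not name recurrence, and the document does not say at what horizon others report it. The benefit for that objective is therefore plausible but not demonstrated.

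**Conclusion.** The concern holds. Recurrence has no time point and no follow-up cut-off, and the stated general rule would yield a percentage that mixes follow-up differing by 3.5 to 4 years. That much rests on the document's dates alone.

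The size rests on assumptions. At a 2-year risk of 30% with even accrual, the pooled figure lies between 25.0% and 32.0% across date readings and hazard shapes. The spurious gap for a 60/40 versus 40/60 mix lies between 0.7 and 5.0 points, and is zero if mix and follow-up are equal. Confidence is high in the omission and lower in the harm to hospital comparisons. This is one outcome in a descriptive sub-study: an inexpensive improvement worth making, not a flaw that undermines the project.

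**What to change.** In the Statistical analysis plan:

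1. State one follow-up cut-off for recurrence. This requires reconciling the 06/30/2017 and 12/31/2017 dates.
2. Define recurrence as cumulative incidence from the date of surgery at a fixed time, censoring at last follow-up and treating death without recurrence as a competing event.
3. Use 1 year for hospitals. Keep 2 years mainly for the pooled registry, since only about half of patients can reach 24 months by 12/31/2017.
4. Compare hospitals on that estimate, with confidence intervals, in place of chi-square on the crude percentage.
5. Report by hospital the surgery-year distribution and follow-up completeness (observed over possible person-time to the horizon).
6. Say that the estimate will be read with caution where event-free patients' last follow-up falls well short of the cut-off, because it is then biased upward.

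The cost is SAP wording and modest extra analysis. Dates of surgery, recurrence, last follow-up and death are already collected and are on the audited list under Audit and validation, so no new data item is needed. The drawbacks are wide intervals in small centers (the sampling rule there provides for centers with 20 or fewer cases) and upward bias where follow-up is not kept current.
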